**C. Study Design and Approach. (RQ-2, RQ-3, RQ-4, RQ-5, RQ-6)**

We will use a three-group randomized trial design to compare the effectiveness of two theory-based interventions to promote completion of CRC screening among individuals at average risk for CRC and, for those who complete colonoscopy, high quality bowel preparation. We will enroll an ethnically diverse group of 450 men and women who canceled, or did not attend, their colonoscopy appointment and randomize them to receive: 1) a tailored DVD intervention; 2) the tailored DVD *plus* a patient navigator intervention; or 3) usual care. The aims of this study are to:

**1. Compare the effectiveness of two interventions designed to promote CRC screening among people at average risk for CRC - a tailored DVD versus the tailored DVD *plus* telephone-based patient navigation - to each other and to usual care.**

Hypothesis 1.1: Participants who receive the tailored DVD *plus* telephone-based patient navigation intervention will have higher rates of colorectal cancer screening with fecal immunochemical test (FIT), colonoscopy, or either screening test compared to those who receive the tailored DVD alone.

Hypothesis 1.2: Participants who receive either intervention will have higher rates of colorectal cancer screening with fecal immunochemical tests (FIT), colonoscopy, or either screening test than those who receive usual care.

[figure not shown]
Hypothesis 1.3: Participants who receive either intervention who complete colonoscopy will have: 1) better quality of bowel preparation; 2) less anxiety about the procedure; and 3) greater satisfaction with the colonoscopy experience than those who receive usual care.

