**Table 3: Data Collection Timeline**

Measures	Baseline Interview (T1)	Process Interview (2 weeks after mailing DVD)	Follow-up Interview at 6 months post-baseline (T2)	Final Interview at 9 months post-baseline (T3)	12 months post-baseline (Final medical record review)
Demographics, social support, media exposure	X				
Health literacy, health status to include co-morbidities	X				
CRC screening experience and readiness to screen, patient activation, health beliefs (perceived CRC risk, benefits of screening, barriers to screening, self-efficacy for screening), CRC fear, cancer fatalism	X		X		
Colonoscopy-related procedural anxiety	X		X	X	
CRC and screening knowledge	X		X		
Receipt, viewing and satisfaction with the DVD		X			
Receipt, experience & satisfaction with the PN			X		
Self-report of CRC screening intention and completion			X	X	
Satisfaction with the screening experience			X	X	
Trial participation feedback				X	
Medical record review: CRC screening test completion, quality of bowel preparation			X	X	X

**C.9. Measures.** The primary study outcomes of CRC screening completion with any test (FIT or colonoscopy), and quality of bowel preparation (for those who complete colonoscopy), colonoscopy-related procedural anxiety and satisfaction with the CRC screening experience are described in this section. Secondary outcomes of the interventions include changes in knowledge and health belief variables (perceived risk, benefits, barriers, and self-efficacy). Other measures include patient activation, CRC fear, cancer fatalism, and satisfaction with the interventions. Measures have been extensively tested and refined in preliminary studies, and are described in more detail elsewhere.

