**PRIMARY OUTCOME MEASURES: (RQ-6, PC-2, IR-4)**

**Completion of any CRC screening test** (fecal immunochemical test (FIT) or colonoscopy) will be measured by medical record review. FIT and colonoscopy completion dates will be extracted from the electronic medical record. Because self-report of CRC screening has correlated well with medical record data, we will also use validated items from our previous research to ask participants if they have had a CRC screening test (FIT or colonoscopy) as well as their plan to have one in the next 6 months (only for those who have not yet completed screening).

**Quality of bowel preparation** will be assessed two ways for those participants who attend their colonoscopy: 1) by participant self-report of their bowel prep experience and 2) via review of electronic medical records. When patients arrive in the endoscopy department, a nurse assesses their experience with the bowel preparation and adherence to dietary restrictions. Patients who report they were unable to complete the bowel prep or have eaten in the past 24 hours are considered inadequately prepped for the procedure and sent home. These patients must repeat the preparation to cleanse the bowel and reschedule their colonoscopy. For those who report successful completion of the bowel prep and adherence to dietary restrictions, quality of the bowel preparation (i.e. degree of cleanliness/emptiness of the bowel) is evaluated by the endoscopist during the colonoscopy. Standard practice is to evaluate bowel preparation quality using an assessment similar to the Aronchick 5-point scale where 1=*excellent*, 2=*good*, 3=*fair*, 4=*poor*, and 5=*inadequate*. Adequate is a term that may also be used to describe the quality of bowel preparation as a single descriptor or in addition to the Aronchick assessment as excellent (1), good (2), or fair (3). Procedural notes including endoscopists' ratings of the quality of the bowel prep are entered into ProVation, a menu-driven software program. Therefore, participants will be considered inadequately prepped if they are: 1) deemed inadequately prepped from self-report during initial nursing assessment OR 2) if the endoscopist rates the quality of the bowel prep as poor (4)

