**C.12. Sample Size, Power Analyses (RQ-2, RQ-4, IR-3).** The revised sample size estimate of 115 per group for analyses is based on ensuring adequate power for Aim 1 (see Table 4). The main objective is to compare the 12-month CRC screening rates with any test among the three groups, so the binary outcome of any CRC screening test completion at 12 months as documented in the electronic medical record has driven calculation of our sample size. For Aim 1, we will first test whether there is any overall group difference in CRC screening completion rates using a chi-square test at 5% significance level. If a significant difference is observed, pairwise comparisons will be conducted at  $\alpha=1.7\%$  (5%/3 pairwise tests) to account for multiple testing. Expected CRC screening rates, based on prior studies demonstrating the effects of computer-tailored and PN interventions, are shown in Tables 1 and 2, respectively. We have revised our DVD only effect calculations from the original estimate of 15.5% to 20% for this group. We originally proposed a DVD only effect size of 15.5% based upon the average effect size of studies listed in Table 1. This 15.5% estimate assumed that the lowest rate observed in the DVD only group might be near 20% ([name], 2015) and lowered that rate even further to 15.5% to be more conservative, as statisticians typically assume very conservative effects when doing power calculations. However, by assuming a value closer to, but still less than the lowest rate observed in the literature for a comparable population (which was 22% seen in [name], 2015 per Table 1), the samples sizes can be reduced to 115 per group for Aim 1. This sample size will afford at least 80% power for all three comparisons per Table 4 below. To allow for an approximate 25% attrition which the project is experiencing as of May 31, 2019 and still have 115 per group for analyses, a total sample size of 450 enrolled subjects is required.

**Table 4. Revising the expected rate in the DVD group to 20% (still smaller than the smallest rate for a tailored intervention in Table 1)**

Comparison	Rates	Sample Size for Groups	Power
PN+DVD vs DVD only	44% vs 20%	115 vs 115	92%
PN+DVD vs Usual Care	44% vs 5%	115 vs 115	99%
DVD only vs Usual Care	20% vs 5%	115 vs 115	80%

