Several studies have shown that patient navigation is an effective method to increase CRC screening rates especially in minority groups with effect sizes shown in Table 2 (average of 33.7). We conservatively estimated a 44% (less than 33.7 + 20 = 54%) effect size for the PN + DVD since we will enroll patients who have previously canceled a screening colonoscopy appointment. For usual care, we used the estimate from [name], 2015 in Table 1 as it is most similar to the proposed study. See Table 5 below for summary. At 12 months, 115 in each group will yield at least 80% power for detecting the pair-wise differences (44% v. 20% v. 5%) in completion rates among the three groups using pair-wise chi-square tests or bivariate logistic regression models and a two-sided  $\alpha=.017$  level. Back-calculation, assuming an attrition rate that is approximately 25% from the sample size needed at 12 months, it requires that we approach 600 eligible subjects to enroll 450 (75% participation rate) and randomly assign them to the three intervention groups (150 per

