**C.13. Data Analyses. (IR-3, IR-5, MD-3, MD-5, HT-1, HT-2, HT-3, HT-4)** Preliminary analyses will compare baseline demographic information across groups using means and standard deviations for continuous variables and frequency distributions for categorical variables. We will adjust for those characteristics in subsequent analyses if significant differences emerge at a conservative level for inclusion of a covariate ( $p < .20$ ). Characteristics of participants who drop out by 9 months will be compared with those who remain to determine what biases may exist. **(MD-4)** The above analyses will be conducted using ANOVA, chi-square tests, or exact or non-parametric equivalents. If there appear to be biases in dropout, we will conduct pattern mixture models analyses to see how the results could change based on the MAR assumption **(IR-5, MD-2, MD-3, MD-5)**. Primary analysis of outcomes will employ an intent-to-treat analysis; all participants will be included regardless of compliance with interventions. The main outcome, CRC screening completion with any test (FIT or colonoscopy) will be extracted from medical records for all participants, including those who drop out or are lost to follow-up. Intervention exposure will be measured and its effects will be accounted for in the intent-to-treat analysis. First, we will know whether participants viewed none, part, or all of the DVD. Second, we will document how many contacts PNs make to or on behalf of participants assigned to that group. These variables (viewed none/part/ or all of the DVD and number of navigator contacts) will be added as covariates in analyses. For all aims, sensitivity analysis will be conducted as needed for each outcome to assess the effects of the model assumptions on the results **(IR-5)**. Assumptions, such as normality of residuals, will be checked and appropriate modifications to the analysis plan applied if needed, such as transformations or use of non-parametric methods. From our prior studies, we expect missing data to be minimal (less than 2%) for subjects during participation. For missing data on scales, we will use mean imputation as long as two-thirds of the questions have been answered (or per validated instrument instructions, if otherwise). **(MD-2, MD-3)**

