For Aim 1, we will test the primary hypothesis related to comparing intervention effects among the three randomized groups (H1.1: PN+DVD vs. DVD only and H1.2: PN+DVD vs. usual care and DVD only vs. usual care) using the outcome of completion of CRC screening using any test at 12 months post-baseline. In addition, quality of bowel preparation, procedural anxiety, and satisfaction with the screening experience will be examined as outcomes. As an initial assessment of CRC screening completion at 12 months, we will use a chi-square test for a 3 x 2 (group by screening completion) contingency table to test whether completion rates differ across groups. If the  $p$ -value for the overall test is significant at the .05 level, pair-wise 2 x 2 tests will be conducted at the  $.05/3 = .017$  level. However, the primary analyses for Aim 1 will involve fitting multivariable logistic regression models of the primary outcome of 12-month CRC screening test completion (yes/no). Independent variables will be group assignment and continuous and categorical individual characteristics. These models will also allow us to investigate intervention effects on CRC screening test completion while adjusting for potential confounders. Group assignment will be coded using dummy variables with usual care as the reference category. For H1.3, quality of bowel preparation will be analyzed for those participants who complete colonoscopy with proportional-odds ordinal logistic regression using an ordinal dependent variable ( $1 = \text{excellent}$ ,  $2 = \text{good}$ ,  $3 = \text{fair}$ ,  $4 = \text{poor}$ ,  $5 = \text{inadequate}$ ). If some outcome categories are sparse, the outcome will be dichotomized into adequate

(*excellent or good*) versus inadequate (*fair, poor, or inadequate*). The outcomes of anxiety and satisfaction are continuous outcomes and will be modeled with linear regression.

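### H1.3 compares bowel preparation only among people who complete colonoscopy after randomisation, so it is not a randomised comparison; the bias is of unknown direction and size, and the plan does not handle it

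*Combined protocol and SAP*

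**What the plan says.** Section C states H1.3 for a subset: "Participants who receive either intervention who complete colonoscopy will have: 1) better quality of bowel preparation". Section C.13 (Aim 1) carries this into the analysis: "quality of bowel preparation will be analyzed for those participants who complete colonoscopy with proportional-odds ordinal logistic regression". Section C.9 ranks the endpoint among the primary study outcomes with the same restriction, "quality of bowel preparation (for those who complete colonoscopy".

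Section C.12 bases its power on "detecting the pair-wise differences (44% v. 20% v. 5%) in completion rates among the three groups". These are rates for any test, FIT or colonoscopy. H1.1 and H1.2 predict that the interventions raise colonoscopy completion as well as FIT.

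Two definitions matter for any repair:

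- **Who is assessed.** Under the primary outcome measures in C.9, patients who arrive without having completed the preparation, or having eaten, are "considered inadequately prepped for the procedure and sent home", and they count as inadequately prepared. The C.13 analysis is limited to completers.
- **What counts as adequate.** C.9 places a rating of fair on the adequate side. The fallback two-category outcome in C.13 places it on the inadequate side.

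**The concern.** Everyone enrolled has already cancelled or missed a colonoscopy. If few come back under usual care and many come back with navigation, the completers in the two arms are different kinds of patient, and randomisation does not balance them. Sections A and B name the unpleasantness of the bowel preparation, and confusion about dietary restrictions, among the reasons people do not complete colonoscopy. A link between attending and preparing well is therefore plausible on the protocol's own account.

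Improving preparation is one of the trial's stated purposes. A difference between completers, or the lack of one, could be read as an effect of the DVD or navigator on preparation when it reflects who turned up. An intervention that works could look useless or harmful, and one that does nothing could look helpful.

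**Working it through.** **1. The planned rates.** C.12 gives 44% (DVD plus navigation), 20% (DVD) and 5% (usual care), with 115 analysed per arm and two-sided alpha 0.017. Power = Φ{[|p1−p2| − 1/n − z·√(2p̄(1−p̄)/n)] / √([p1(1−p1)+p2(1−p2)]/n)}, where z is the two-sided critical value and 1/n the continuity correction. This gives 92.2% (44 v 20), above 99.9% (44 v 5) and 80.9% (20 v 5), against 92%, 99% and 80% in Table 4. The rates used below are thus the ones the design rests on.

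**2. How far the completer groups differ.** If every screening test were a colonoscopy (the upper bound), expected completers among 150 per arm are 150 × 0.44 = 66, 150 × 0.20 = 30 and 150 × 0.05 = 7.5. If nobody is deterred by an intervention, 1 − 5/44 = 89% of DVD-plus-navigation completers and 1 − 5/20 = 75% of DVD completers would not have completed under usual care.

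**3. Apparent effect when the true effect is zero.** Let completing and preparing adequately be two correlated standard normal traits. Then P(adequate | complete) = Φ₂(z_c, z_a; r)/p_c, where p_c is the completion rate, z_c = Φ⁻¹(p_c) and z_a = Φ⁻¹(0.70). The 70% is an assumption. It is suggested by section A's figure of up to 30% inadequate, but that figure refers to attenders. The correlation r is also assumed; the documents give none.

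| r | 44% completing | 20% | 18% | 5% | Gap, 44% v 5% | Gap, 44% v 18% |
|---|---|---|---|---|---|---|
| 0 | 70.0% | 70.0% | 70.0% | 70.0% | 0 | 0 |
| 0.2 | 76.2% | 79.3% | 79.7% | 83.0% | 6.8 points | 3.4 points |
| 0.3 | 79.3% | 83.6% | 84.1% | 88.3% | 9.0 points | 4.7 points |
| 0.5 | 85.7% | 91.4% | 92.0% | 96.1% | 10.4 points | 6.3 points |

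The 18% column uses the usual-care rate that section B.1 reports at 6 months from an earlier tablet-based trial in the same health system. Setting 70% adequate among usual-care completers instead gives 61% v 70% at r = 0.2 and 56% v 70% at r = 0.3, so that choice does not shrink the gap.

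**4. Direction when the intervention truly helps.** Assume a 20% relative reduction in inadequate preparation. Let q0 be the untreated risk of inadequate preparation in people who would complete anyway, and q1 the risk in those brought in. For DVD plus navigation, observed inadequate = 0.8 × [(5/44)q0 + (39/44)q1], compared with q0 under usual care.

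| q0 | q1 | Observed inadequate | Odds ratio v usual care |
|---|---|---|---|
| 15% | 30% | 22.6% | 1.66 |
| 20% | 25% | 19.5% | 0.97 |
| 30% | 30% | 24.0% | 0.74 (no selection bias) |
| 30% | 25% | 20.5% | 0.60 (benefit exaggerated) |

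The sign reverses once q1/q0 exceeds (1/0.8 − 5/44)/(39/44) = 1.28. For DVD alone the threshold is (1/0.8 − 0.25)/0.75 = 1.33.

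**5. Does the plan handle it elsewhere?** The dropout comparison and pattern-mixture models in C.13 concern attrition. The covariates are baseline characteristics that differ between randomised groups at p < .20, plus intervention exposure; neither targets selection into colonoscopy. Sensitivity analyses are left to be done as needed. The sample-bias item in C.14 concerns who enrols. Counting sent-home attenders as inadequate widens the group slightly, but attending is also a post-randomisation event.

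**The case against.** Four points on the other side carry weight.

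- **Direction.** A reader might infer that the comparison is biased against the more successful arm. The documents do not support that. It follows only if one motivation trait drives both attending and cleansing, and r has no source. There is also a route the other way: the DVD presents FIT as an alternative (C.4.a) and navigators mail a FIT on request (C.4.b). Reluctant patients in the intervention arms may leave the completer group, so that those who remain actively chose colonoscopy. This stands.
- **Conflict with intention to treat.** C.13 says "Primary analysis of outcomes will employ an intent-to-treat analysis; all participants will be included regardless of compliance with interventions", and a reader might see a contradiction. The sentence concerns compliance with the interventions, and having a colonoscopy is an outcome. C.9, H1.3 and C.13 all state the completer restriction openly. The weakness is the comparison chosen, not an inconsistency in the text.
- **A false finding of harm.** With 66 v 8 completers and the spurious gaps at 44% v 5%, the chance of a significant harmful result (Fisher exact test, two-sided 0.05) is 0.3% at r = 0.2, 0.09% at r = 0.3 and below 0.01% at r = 0.5. A formal harm conclusion is very unlikely. The practical risk is a misread estimate or a misread null, and the small numbers would contribute much to a null.
- **The all-randomised composite as the H1.3 test.** It would not test preparation. In the zero-effect scenarios with r = 0.2 to 0.5, completion times adequacy gives 33.5% to 37.7% v 4.1% to 4.8% for DVD plus navigation v usual care. With 150 per arm and alpha 0.017, without continuity correction, power is above 99.9%; for DVD v usual care it is 84% to 90%. The composite would nearly always succeed with no preparation effect at all.

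None of this restores the randomised comparison.

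**Conclusion.** The concern holds as a structural point. It follows from H1.3 and C.13 alone: the analysis set is defined by an event that the trial expects to differ by arm, and nothing in the plan addresses that.

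The size and sign of the bias cannot be settled from the documents. The 7-to-10-point and 3-to-6-point figures are illustrations. They assume a positive latent correlation of 0.2 to 0.5, 70% adequate overall, any-test rates standing in for colonoscopy, and no FIT-driven change in who completes. At zero correlation the gap is nil, and it could favour the interventions. The supportable conclusion is that a difference between completers, in either direction, cannot be attributed to the interventions' effect on preparation.

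**What to change.** In C.13:

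1. Label the completers-only bowel-preparation analysis as non-randomised and descriptive, with no claim of superiority or harm.
2. Pre-specify a sensitivity analysis for the selection, either bounds or a principal-stratum analysis, with its assumptions stated.
3. Add a supplementary outcome in all randomised participants: colonoscopy completed with adequate preparation by 12 months, yes or no, with non-completers counted as no. State beside it that it mainly reflects completion and is not evidence of better preparation quality.
4. Use one definition of adequate throughout, after reconciling C.9 and C.13 on the fair rating. Also reconcile whether attenders who are sent home belong to the completer analysis.

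The cost is small. The electronic record review already covers screening completion and preparation quality up to 12 months, so no new data collection is needed. The price is slightly more analysis work and a weaker permitted conclusion for H1.3.

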**2. Examine age, race/ethnicity, sex, and income as potential moderators of intervention effects. (RQ-4)**

**3. Examine changes in knowledge and health beliefs (perceived risk, perceived benefits, perceived barriers, and self-efficacy) as potential mediators of intervention effects. (RQ-6)**

[figure not shown]
Both interventions can serve as adjuncts in any existing health care system to facilitate completion of CRC screening and improve the quality of bowel preparation. A number of complex factors may contribute to low CRC screening completion rates after provider referral, but more work is needed to understand these factors. We will explore whether the effects of these interventions differ for various subgroups of participants. Heterogeneity of treatment effects will be determined by examining age, sex, and race/ethnicity as potential moderators. **(HT-1)**

Figure 1. Conceptual Model Adapted from Warnecke, et al. 2008

**C.1. Conceptual Model.** The model guiding this study was adapted from Warnecke and colleagues (Figure 1). This multilevel model shows the proximal, intermediate, and distal determinants of health that will be targeted by the interventions. Consistent with this model, we will test a telephone-based patient navigation intervention that will provide social support (social relationships) and access to community resources (physical context) for people who have been scheduled for colonoscopy. Specifically, the patient navigators (PNs) will provide individualized support based on assessment of demographics, knowledge, health beliefs, and barriers. By interacting with the health care system and community resources, they will assist patients to overcome their unique logistical and other barriers to CRC screening. A tailored DVD titled “*Time to ACT: Approaches to Colon Testing*” will be designed to increase knowledge, health beliefs, and self-efficacy for CRC screening.

**C.2. Design.** A three-group randomized controlled trial will be conducted to compare the effectiveness of two interventions to promote CRC screening test completion. Eligible men and women who were scheduled for colonoscopy in the endoscopy unit at Eskenazi Health (our safety net health system) but did not attend their appointment will be invited to participate. After baseline data are collected via structured telephone interviews, participants will be randomized to receive: 1) a mailed DVD titled *Time to ACT: Approaches to Colon Testing*; 2) the mailed DVD plus a patient navigator (PN) intervention; or 3) usual care (See Figure 2). (RQ-2, RQ-3, RQ-4, RQ-5)

Study Design and Schema

**C.3. Setting and Recruitment. (PC-2)** On a weekly basis, Eskenazi Health IT department will generate lists of age-eligible patients at average risk who did not attend their colonoscopy appointment. The list will include 2 groups of average risk patients who missed their appointment: 1) patients who had a colonoscopy screening ordered; and 2) patients who had a recent fecal immunochemical test (FIT) that was positive with a follow-up order for colonoscopy. Due to differences in physician ordering practices, the follow-up colonoscopy can be ordered as a colonoscopy screening, colonoscopy diagnostic, or colonoscopy high risk. Patients will be approved for contact by [name], Director of the Eskenazi Health Endoscopy Department. Patient information will be released to the study’s data manager, the Eskenazi Endoscopy Department’s Patient Navigator nurse, and trained research staff at the IU School of Nursing using secure electronic data transfer methods. Information disclosed is limited to that which is necessary to determine eligibility and to contact patients by mail and telephone. As a first step, the Endoscopy Patient Navigator nurse or nurse designee will screen patients by looking back 10 years and excluding any with a history of adenomatous polyps, sessile serrated polyps, or any mass suggestive of neoplasia. Patients with a history of hyperplastic polyps, lymphoid tissue, or no polyps will be

recruited. To be eligible, these patients must: 1) have been referred for a colonoscopy that was not done (i.e, canceled or no show); and 2) be 50 to 75 years old if non-African American or 45-75 years old if African American. Patients meeting these inclusion criteria will be excluded for the following reasons: 1) unable to speak, read, and write English; 2) a personal history of having a colonoscopy at a non-Eskenazi Health location where polyps were found and they were the type that could turn into cancer; 3) FIT negative result in the past 12 months; 4) a personal history of CRC; 5) a personal history of conditions that place them at high risk for CRC such as ulcerative colitis, Crohn's disease, or known hereditary syndromes such as familial adenomatous polyposis or hereditary nonpolyposis colorectal cancer; 6) a family history of CRC which increases their risk; and 7) speech, hearing, cognitive, and/vision impairment. Trained research staff at the IU School of Nursing will recruit patients using procedures consistent with clinic and HIPAA requirements. Recruiters will send introductory letters, signed by the Principal Investigator and a co-investigator who is a member of the Eskenazi Medical Staff, along with a recruitment brochure and Study Information Sheet that explains the study to all approved patients. The letter informs patients that they will receive a phone call about the study within the next week unless they call a toll-free number to say they do not wish to be contacted. One week after letters are mailed, trained recruiters at the IU School of Nursing will call potentially eligible participants who have not opted-out to explain the study requirements, potential risks and compensation, and answer questions. Adequate speech, hearing, and cognition of potential participants will be confirmed by recruiters based upon the phone conversation. They will then proceed to determine eligibility, obtain both verbal informed consent and verbal HIPAA Authorization, and schedule a convenient time to conduct the baseline interview. Each participant who is not reached will be called back up to, but no more than, 10 times. Recruiters will record each call attempt including the date, time, disposition, and callback preference. Participants who decline to participate will be thanked for their time, with their response and reason for refusal recorded.

Re-contact efforts will be attempted for patients who were originally excluded from the study due to reporting a history of colon polyps (histology type unspecified). Amendment 013, approved by the IRB last year on 5/30/2018, allows patients with a history of benign colon polyps to be included in the study. The Endoscopy Patient Navigator nurse or nurse designee will review the records of these previously excluded patients to determine if: (1) the polyp histology type was benign; and (2) a colonoscopy is still needed. Patients with benign polyps who are due for a colonoscopy will be re-contacted following the usual recruitment procedures described above. A slightly modified version of the study introductory letter which notes in the opening paragraph that patients may now be eligible will be used in lieu of the standard introductory letter.

Additionally, re-contact efforts will be attempted for patients who previously gave their verbal consent to participate but failed to return the written informed consent and HIPAA Authorization in order to be officially enrolled. The IRB approved a change to the protocol on 11/27/2018 which discontinued the requirement for informed consent and HIPAA Authorization to be obtained in writing. These patients may now be willing to be enrolled since written forms do not need to be completed and returned to the research office. This cohort of patients will be re-contacted following the usual recruitment procedures described above. A slightly modified version of the study introductory letter which explains in the opening paragraph that written consent forms are no longer required for enrollment will be used in lieu of the standard introductory letter.

[figure not shown]
**C.4. Intervention and Usual Care Descriptions. (PC-1, PC-2, PC-3, RQ-2, RQ-5).** The tailored DVD titled *"Time to ACT: Approaches to Colon Testing"* and patient navigator interventions are described in the following sections. All phases of intervention refinement will be conducted in consultation with our Community Advisory Board, which will be comprised of 8 members of the target population. Our Community Advisory Board (CAB), [name], our patient stakeholder and Chair of the CAB, and [name], Director of the Indiana University Simon Cancer Center's Office of Health Disparities and Community Engagement, will ensure the relevance of both interventions to a diverse group of users. By interacting with the patient navigator, participants will receive a barrier-reducing intervention that will be individualized based on their knowledge, health beliefs about CRC screening, and identified logistical barriers. The tailored DVD addresses these same theoretical concepts and will incorporate colors, screen designs, and music preferred by our CAB. Usual care in the Eskenazi Health System endoscopy department begins with referrals for screening

colonoscopy that are generated by primary care providers in this integrated health system. Primary care providers enter colonoscopy orders into the electronic health record which are immediately communicated to the endoscopy department. Endoscopy department staff schedule an appointment, typically within 4-5 weeks of the referral, and mail an information packet about the procedure along with written instructions for completing the bowel preparation. The packet includes instructions to call with any questions and if necessary, to reschedule the appointment. Within 1-2 days prior to the scheduled appointment, an endoscopy department nurse telephones each patient to remind him/her of their appointment and answer any questions about the procedure, including completing the bowel preparation.

**C.4.a Tailored DVD.** The 20 minute tailored DVD will be refined during the first 11 months in collaboration with Eo Studios in Athens, Georgia. The tailored DVD will be an expansion of our prior work in which we developed and tested a computer tablet-based tailored intervention to promote CRC screening in primary care settings (1R01-CA115983; [name], PI). For that study, we collaborated with Eo Studios, an experienced production company, to create a computer program with graphics, animations, video clips, and audio clips that were specifically targeted to African Americans. The program incorporated narrative colors, screen designs, and music preferred by our Community Advisory Board who worked with us on that study. Because some members of our target audience had limited health literacy, the program was completely narrated and required minimal reading. Some graphs, animations, videos, still images, and narrated messages from that interactive program will be used to refine/expand the new DVD program. However, we will need to adapt the existing program for a broader audience. Although we have video and audio clips of testimonials from people who overcame common barriers to CRC screening, we will need to develop segments that demonstrate the newer fecal immunochemical test (FIT) and update instructions for completing the bowel preparation. Simple and clear instructions, with illustrations, video clips, audio clips and animations will be developed for split-dosing of GoLYTELY® and Miralax, the two most common bowel preparations prescribed at Eskenazi. We have approximately 200 unique photographs acquired from on-site photography/videography and digital imaging libraries available from our prior studies. We also have a large number of audio clips that will be incorporated along with full-motion video clips demonstrating CRC screening tests, steps for completing them, and key testimonials. Additional graphics, video, and animations will be designed by Eo Studios. Animation will be incorporated in a variety of ways. For example, animation will be used within charts or graphs developed to illustrate CRC risk and animated icons and sound will be incorporated throughout the program to enhance the look, feel, consistency, and usability of the program. Our patient stakeholders (CAB members) will guide refinement of the tailored DVD. **(PC-1, PC-3)**

Figure 3. DVD CONTENT & FLOW

The DVD content and flow are shown in Figure 3. After a brief introduction to the purpose of the DVD, the narrator will explain the location of the colon, what it does, and how colon cancer develops from polyps. The program will describe the benefits of CRC screening and two commonly used screening tests: colonoscopy and the fecal immunochemical test (FIT) which is a type of stool blood test. Barriers that people may have about screening tests will be assessed and messages delivered to overcome these barriers. Messages will be delivered by men and women who are CRC survivors and CRC screening advocates who vary in race and ethnicity. The DVD will provide demonstrations of each screening test, dietary restrictions, and the steps to complete them. All information will be presented with graphics, video demonstrations, and animations to accompany the narration. The goal will be to make the content easy to find and navigate. Minimal navigation expertise will be necessary. Once the “Play” button is selected by the viewer, the program will automatically advance. Selected sections of the program will be available for re-playing by using the DVD Menu. The overarching intent of the study is to create both English and Spanish versions of the DVD. However, development of the English version will take precedence due to time constraints by Eo Studios, our design firm. We will open the study using the English version only and require that participants be able to speak, read, and write English in order to be eligible for enrollment. Development of the Spanish version will occur in 2018. When the Spanish version is completed, we will submit an Amendment to the IRB, along with the necessary accompanying documents, to offer the study to Spanish speaking patients. (PC-2, PC-4).

**C.4.b. Telephone-based Patient Navigation Intervention.** The telephone based intervention has been developed and tested in prior research by our Ohio State University team members. Patient navigation (PN) also supplements face-to-face clinical encounters with primary care providers and extends the limited time devoted to preventive care and health counseling. The proposed telephone PN intervention is theory-based and will be designed to: 1) increase knowledge, perceived benefits, and self-efficacy; 2) reduce barriers; 3) enhance access; and 4) provide social support. Theoretical constructs, objectives, and content of the PN interactions (minimum of two) are described elsewhere. Development of the web-based navigator protocol and documentation system (tracking log) will occur in collaboration with our biostatisticians and expert data manager. The goal of the protocol will be to guide trained PNs to counsel participants by telephone within a standardized framework. The protocol will serve as a counseling guide but will allow navigators flexibility to individualize contacts based on a participant’s expressed needs and concerns. The interface will provide prompts to assist PNs and allow them to document all encounters with, and on behalf of, participants.

